J1	Complete 75% of follow- up data collection	675 participants finish 4-month acute phase and 12-month continuation phase (estimate of 12-month completers = 675, based on 45% of participants remitting at each of steps 1 and 2, 8% of participants dropping out during each of steps 1 and 2, and additional 10% dropping out during the 1-year continuation phase). The Interim Progress Report should include summary of data collected to date for review of patient accrual, patient characteristics and data quality.	1/1/2021
J2	DSMB meeting	Minutes from 9th DSMB meeting. Review and discuss subject data collected to date. In the interim progress report, include any significant data & safety monitoring issues that occurred in the reporting period. If there are any serious unanticipated problems (e.g., serious adverse event, serious safety issue, or other serious problem) relating to the research study, awardee institutions must notify PCORI promptly, but no later than 10 days after.	4/1/2021
13	Stakeholder Advisory Board Meeting	Stakeholder Advisory Board Meeting. Deliverables: Meeting minutes and/or summary of the meeting discussion should document the input of the patient/stakeholder members and should be submitted with the Interim Progress Report	4/1/2021
	Report Submission	Submit Progress Report, Using Interim Progress Report Template	4/1/2021

_			
K1	Complete follow-up data collection	All (n=900) participants finish 12-month continuation phase (estimate based on 45% of participants remitting at each of steps 1 and 2, 8% of participants dropping out during each of steps 1 and 2, and additional 10% dropping out during the 1-year continuation phase). The Interim Progress Report should include summary of data collected to date for review of patient accrual, patient characteristics and data quality.	9/1/2021
K2	Primary Research Completion Date	A Primary Research Completion Date must be provided when registering the study in Clinicaltrials.gov. For studies that are not clinical trials or observational studies registered on ClinicalTrials.gov, the Awardee and PCORI shall agree on a primary completion date as a milestone that precedes the agreed-upon date to submit a Draft Final Research Report.	9/1/2021
К3	Initiate data analyses	Clean database and set up analytic files	9/1/2021
K4	Complete data analyses	"Break blind" and run analytic files	9/1/2021
K5	Final DSMB meeting	Minutes from 10th DSMB meeting. Review and discuss subject data collected to date. In the interim progress report, include any significant data & safety monitoring issues that occurred in the reporting period. If there are any serious unanticipated problems (e.g., serious adverse event, serious safety issue, or other serious problem) relating to the research study, awardee institutions must notify PCORI promptly, but no later than 10 days after.	9/30/2021
К6	Stakeholder Advisory Board Meeting	Stakeholder Advisory Board Meeting. Deliverables: Meeting minutes and/or summary of the meeting discussion should document the input of the patient/stakeholder members and should be submitted with the Interim Progress Report	9/30/2021
K7	Dissemination and implementation	Prepare findings for D&I	9/30/2021
K8	Data sharing	Begin preparation of de-identified final dataset for replication and data-sharing. Prepare results for publication in peer-reviewed journals and submission of results to clinicaltrials.gov	9/30/2021
К	Final Progress Report	Submit Final Progress Report, Using Final Progress Report Template	9/30/2021
L	Research Project Period End Date		9/30/2021
Μ	Results submitted to ClinicalTrials.gov or appropriate database.	Awardee ensures results are submitted to ClinicalTrials.gov or appropriate database. For ClinicalTrials.gov, the generated tables are a required section in the Draft Final Research Report.	12/1/2021
N	Draft Final Research Report Submission	Submit Draft Final Research Report according to instructions found at http://www.pcori.org/awardee-resourcesx *Draft Final Research Report must be submitted no later than 30 days from when results are posted to clinicaltrials.gov or other applicable website.	1/1/2022
0	Final Research Report	Upon receipt of written summary, and as applicable, PI will make revisions and submit revised Draft Final Research Report for acceptance as directed by PCORI.	See Description
Р	Approval / sign off of the Lay Abstract	Sign off must be no later than 90 days beyond the date PCORI accepts the final report	See Description
Q	Contract Term Date	-	5/31/2022
R	Final Expenditure Report	Submit Final Expenditure Report (See Contract for Instructions)	90 days from Contract Term Date
s	Notification of	See Contract for Instructions	Within 30 Days

K5 History of Changes to Study Protocol

Version number and date	Description of changes
V2.3: 1/19/17	Originally approved version of the study protocol.
V2.4: 3/31/17	Participants who do not qualify for Step 1 due to a contraindication to a Step 1 medication, but otherwise meet eligibility criteria, may participate and proceed directly to Step 2.
	 Increase in maximum dose of bupropion from 300 mg to 450 mg to be consistent with the FDA approved maximum dose.
	3) Additional baseline assessments.
	4) Assessment of falls at every decision support.
	Collection of self-reported weight at baseline, acute phase end, and continuation time points.
	6) All participants followed in Continuation, not just remitters.
	 NIH Cognitive and Motor Batteries assessed at Continuation Month 12 but not at 4 or 8.
	8) DNA samples collected via saliva sample instead of blood.
V2.5: 6/26/17	 Changes to eligibility criteria. Seizure disorder and Parkinson's disease are exclusions for Step 1 but not for Step 2.
	 Clarification to Step 2 exclusions indicating that participants may still be considered for Step 1 participation even if ineligible for Step 2.
	 Clarification to lithium augmentation prescribing information that levels outside of 0.4 – 0.8 mEq/L window may still be acceptable per PI discretion.
	 Clarification to nortriptyline switch prescribing information that levels outside 80-120 ng/ml window may still be acceptable per PI discretion.
	 Removed fasting glucose from (generally) recommended baseline labs and added new section for recommended labs prior to aripiprazole augmentation including fasting glucose and fasting lipid panel.
V2.6: 10/2/17	 Clarified Step 2 exclusion of Acute or chronic renal insufficiency with the addition of the following language: as indicated by creatinine clearance below 30 mL/min; suspected if creatinine above 1.5 mg/dL; per PI and/or clinician discretion.
V2.7: 10/31/17	 Updates to assessment procedures: a. If there is a long delay between the Step 1 Week 10 assessment and the initiation of Step 2, the participant may be asked to repeat some or all of the Step 1 End assessments. b. Participants who relapse in Continuation after Step 1 may be invited to participate in Step 2; and then continuation subsequently.
	 Addition of qualitative interviews for randomly selected subset of participants to fulfill Aim 3.
V2.8: 12/5/17	 Narrowed Step 2 exclusion criteria to identify and exclude patients with active ischemic heart disease while including patients with history but no symptoms for the past 2 years.

V2.9: 3/26/18	 Addition of body composition measurement at WU.
V3.0: 3/4/19	1) All participants are to begin the study in Step 1. Following their
	participation in Step 1, they will be considered for Step 2 (as in the
	current protocol). However they will not be invited to participate in
	Step 2 without first participating in Step 1.
	a) Accordingly, because direct entry into Step 2 is disallowed, the Step
	1 exclusions of Seizure disorder and Parkinson's Disease are
	exclusions to the study as a whole.
	2) Increasing the inclusion criteria for the PHQ-9 from 6 to 10 to include
	participants with higher degree of symptom severity.
	3) Recommended schedule for standard of care follow-up labs is being
	standardized in the protocol.
	4) Removal of body composition measurement. This was exploratory
	and is not safety related.

References

- 3. PCORI. Prioritizing Comparative Effectiveness Research Questions for the Treatment of Major Depressive Disorder: A Stakeholder Workshop Meeting Summary. 2015. http://www.pcori.org/sites/default/files/PCORI-Prioritizing-CER-Questions-Stakeholder-Workshop-Depressive-Disorder-Meeting-Summary-060915.pdf.

5.1. Screening data	
5.2. Eligibility	
5.2.1. Inclusion Criteria (Steps 1 & 2	2)
5.2.2. Exclusion Criteria (Steps 1 &	2)
5.2.3. Exclusions to Enter Step 2	

5.3. Recruitment	10
5.4. Withdrawal/follow-up	10
5.4.1. General withdrawal rules	10
5.5. Baseline participant characteristics	11
5.5.1. List of baseline characteristics	11
5.5.2. Descriptive summarization of baseline participant characteristics	11
6. Analysis	12
6.1. Outcome definitions	12
6.1.1. Primary and secondary outcomes	12
6.1.2. Outcome measurements	12
6.2. Analysis methods	13
6.3. Missing data	13
6.5. Harms	14
6.6. Statistical software	14

Abbreviation

*ADM Antidepressant Medication

AE Adverse Event

ATHF Antidepressant Treatment History Form

*CFR Code of Federal Regulations

CIRS-G Cumulative Illness Rating Scale-Geriatric

DAST-10 Drug Abuse Screening Test

DSMB Data Safety and Monitoring Board

EMR Electronic Medical Record
*E-CRF Electronic Case Report Form

EKG/ECG Electrocardiogram

*FDA Food and Drug Administration

GCP Good Clinical Practice

*HIPAA Health Insurance Portability and Accountability Act

*ICF Informed Consent Form IRB Institutional Review board

ITT Intention-to-treat

MADRS Montgomery-Asberg Depression Rating Scale
MD – (1-5) Standards for Preventing and Handling Missing Data

MDD Major Depressive Disorder MDE Major Depressive Episode

MINI Mini-International Neuropsychiatric Interview

*NMS Neuroleptic Malignant Syndrome

OPTIMUM Optimizing Outcomes of Treatment-Resistant Depression in Older Adults

PCORI Patient Centered Outcomes Research Institute

PHQ-9 Patient Healthcare Questionnaire

PI Principal Investigator

PROMIS Patient Reported Outcome Measurement Information System

RCT Randomized Controlled Trial
REDCap Research Electronic Data Capture
SAB Stakeholder Advisory Board

SAE Serious Adverse Event

TRD Treatment-Resistant Depression

^{*}Appeared in the protocol, but not in the SAP

2. Introduction

2.1. Background and Rationale:

One-half or more of older adults fail to remit with antidepressant pharmacotherapy. Treatment-resistant depression (TRD) in older adults is highly deleterious because persistence of depression is a leading cause of disability, suicide, dementia, and premature mortality. Making it worse is the lack of evidence-supported treatments at a stage in life when medications' benefit vs. risk ratio crucial.

The Optimizing Outcomes of Treatment-Resistant Depression in Older Adults (OPTIMUM) study will provide the evidence that older adults need to get an effective treatment that works best for them, improving their quality of life while minimizing risks of medications.

2.2. Objectives

2.2.1. Objectives and study aims

The study aims to close the evidence gap on late-life depression in three ways. First, we will examine the comparative benefits and risks of antidepressant strategies (augmentation and switching) in older adults with TRD. In addition to looking at rates of depression remission, we will focus on the effects on the outcomes that also matter to older adults, like well-being, adverse events, and falls. Secondly, we will explore how aging changes the balance of benefits vs. risks. With aging comes a decline in brain and systemic health that may alter the benefit/risk ratio of antidepressant strategies. Third, we will maximize stakeholder engagement by conducting semi-structured qualitative interviews of patients and providers and convening a Stakeholder Advisory Board (SAB) to guide the study and ensure its relevance to patients and providers Armed with the knowledge of differential benefits and risks, stakeholders could provide personalized precision care that maximizes the benefits of TRD treatment strategies for older adults with minimizing risks.

2.2.2. Hypothesis

Theme 1: Benefits and risks of antidepressants: outcomes that matter for patients and clinicians

- 1. Effectiveness. Augmentation arms will show greater improvement than monotherapy arms for effectiveness outcomes.
 - a. Wellness outcome: Improved psychological well-being. (H1a)
 - b. Symptom outcome: Remission from depression (defined as MADRS ≤10 at Step end).
 (H1b)
- 2. Safety. Augmentation arms will have more tolerability and safety concerns (i.e., more serious adverse events) than monotherapy arms.
 - a. Serious adverse events (H2a), falls, and fall-related injuries (H2b) are the safety outcomes.

The primary analytic strategy is a test of specific treatment strategies (e.g., aripiprazole augmentation). More recently, a report on these strategies in mixed-age veterans with TRD (Mohamed et al, JAMA 2017) has suggested that augmentation approaches yield higher remission rates than does switch. The TRD field has, likewise, converged on the overarching question of whether augmentation is superior to switch, more so than the specific question of which augmentation approach is superior (e.g., Ruberto, Jha, & Murrough, "Pharmacological treatments for patients with treatment-resistant depression", Pharmaceuticals 2020; Voineskos, Daskalakis & Blumberger, "Management of treatment-resistant depression", Neuropsychiatr Dis Treat 2020) with a recent Cochrane systematic review (Davies et al, 2019) determining that augmentation strategies appeared efficacious while switch strategies had uncertain efficacy.

For this reason, a secondary analysis of each hypothesis will test the overall strategy of augmentation vs. switch. The two augmentation arms in Step 1 will be summed and compared to the switch arm.

Theme 2: Aging influences the balance of benefits and risks of antidepressant strategies.

3. Moderator analyses (Heterogeneity of Treatment Effect). Exploratory analysis (HT-1): Effectiveness and safety differences between treatment arms will be moderated by age. Specifically, with increasing age effectiveness differences between treatment arms will decrease, and safety differences between treatment arms will increase. In addition, the following potential moderators will be assessed: executive function, co-morbid medical burden, co-morbid anxiety, and degree of treatment resistance.

2.2.3. Scope

This Statistical Analysis Plan will be the guiding document for the quantitative analyses that will be conducted in the OPTIMUM study.

3. Study Methods

3.1. General Study Design and Plan:

Participants will be recruited from five regions with diverse and representative populations encompassing approximately 708 adults. The five regions are: St. Louis and rural Missouri; Los Angeles City and County; Pittsburgh and Western Pennsylvania; New York City; and Toronto and rural Ontario. Participants will be non-demented adults aged 60+, with equal proportions aged 60-70 and 70+, with current major depression that has failed to respond to 2+ adequate antidepressant trials. Two-thirds of the sample will be women and 86% White, 7% Black, 8% Latino/Hispanic, and 4% other racial groups.

All recruited adults will be randomized to 10 weeks of one of three Step 1 strategies: aripiprazole augmentation, bupropion augmentation, or switch to bupropion. Those who do not attain remission in Step 1 or those who do not qualify for Step 1 will be randomized to 10 weeks of one of two Step 2 strategies: lithium augmentation or switch to nortriptyline. Those who complete acute treatment will be followed in a one-year continuation, with assessments every four months. This pragmatic RCT will be carried out in real-world clinical settings. Primary care and mental health clinical partners will provide treatments, with decision support from the study team.

Patients will be identified from clinical networks at each of the five participating centers. Our two primary mechanisms of recruitment will be through screening and referrals. We will screen through clinical networks using Electronic Medical Records (EMR) and will contact all patients in practices aged 60 and older who in the recent past were prescribed or are currently taking antidepressants. Referrals will be elicited from practitioners and through advertisements to patients and their caregivers.

An additional mechanism of recruitment will be through IRB-approved hospital network registries and social media advertisements and posts on Facebook and Instagram. Potential participants who see Facebook ads and want to participate in the study can click on the Facebook ad and it will direct them to a secure and encrypted survey website using Redcap to collect name, phone number, and email address. Research study staff will contact the potential participants to screen them for study eligibility.

3.2. Randomization

Randomization of participants will be implemented in REDCap, using a randomized block design by alternating blocks of 3 and 6 within strata by site (i.e., St Louis vs. Pittsburgh), referral source (primary care vs. specialty mental health) and age (<70 vs >70).

Only assessors of outcome measures will be blinded. Assessors will be instructed to not ask, and participants instructed to not share the treatment to which they were assigned. Participants, providers, and other research staff will not be blinded to treatment conditions.

In this pragmatic design where all levels of adherence are allowed, participants will be considered randomized assuming they meet the eligibility requirements at screening (including any safety screens as applicable) and they have been given a randomization assignment (i.e., even if participants never took a dose of the randomized medication, they will be included in the analysis).

3.3. Sample Size

Our original proposal was to randomize 1,500 patients in Step 1 and 800 for Step 2. This was adjusted mid-study when it became clear that recruitment efforts would not achieve this sample size. Newly adjusted sample size is 708 (estimated mid-study), including 123 participants who were enrolled into step 2 without first participating in step 1.

3.4. Framework

Hypothesis testing framework: H₀ and H₁ with confidence intervals for differences.

3.5. Statistical interim analyses and stopping guidance

No interim analysis is planned. As there is no placebo and all treatments are FDA-approved and frequently used in older adult, no contingency plans for early stopping because of futility or safety are planned.

3.6. Timing of final analysis

Analyses will ensue after recruitment is completed and all participants have finished their acute phase.

This statistical analysis plan was added to the study protocol at clinicaltrials.gov, before the closure of the database and before any analyses had been conducted. Independent study monitoring was conducted in adherence to the Good Clinical Practice(GCP) guidelines. The statistician will be blind to treatment assignments during the analysis.

3.7. Timing of outcome assessment

Outcome assessment will be conducted at the end of the acute phase for both step 1 and step 2. During the continuation phase, assessments will be conducted at month 4, month 8, and month 12.

4. Statistical principles

4.1. Confidence intervals and p values

To test our primary hypothesis (H1a), a significance level of .05/3 will be considered as statistically significant in Step 1. A significance level of .05 will be considered statistically significant in Step 2. If the significance level is greater than .05, we will emphasis the increased chance of a type I error. Results will be presented with their values (e.g. regression coefficients, standard deviation, etc.) with 95% confidence intervals.

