6.2. Analysis methods

To test hypothesis H1a (psychological well-being), a repeated measure of 2*2*3 ANOVA with age (60 – 70, > 70), time (baseline, end of Active phase of Step 1) by treatment group (3 levels) will be used. Specific time * treatment group contrasts will compare the changes across pairs of treatment groups. These tests will be conducted with a Hochberg Step-down procedure. If the comparison with the lowest p-value < 0.05/3 it is significant. If the second lowest p-value is also < 0.05/2 then it also will be significant and if the third p-value is < 0.05 then it also will be significant. We will include site as strata in all analyses. For those who proceed to Step 2, analogous repeated measures 2*2*2 ANOVA will be used with a significance level of .05 for the time*treatment group comparison.

To test hypothesis H1b (remission), a corresponding 2*3 (age by treatment group) generalized linear models with a logit link function will be computed for the dichotomous outcome of remission. Pairwise treatment groups will be compared as in H1a.

To test hypothesis H2a (serious adverse events), Cox models will be used to examine time to event (with Anderson & Grill extensions for repeated events) will compare the treatment arms during both the acute phase and the continuation in terms of serious adverse events. Pairwise comparison between treatment groups will be tested.

To test hypothesis H2b (falls and fall-related injuries), a repeated measures generalized linear model with a cumulative logistic link function. The factors will be treatment group and time (week 2, 4, 6, 8 or 10). The age group (<70 vs.>70) and clinic stratification variables will be included in the model as well as the fall history obtained at baseline. Pairwise comparisons between the treatment group pairs will be formally tested. The same model with a simple logistic link function will be conducted during each 2-week period where the response is a fall-related injury or not.

In terms of the exploratory hypothesis 3, we will include the treatment by age group (<70 vs >70) by time interaction to the linear models described above to test for both the benefits and risks for the treatment alternatives. Additionally, we will fit a model with age as a continuous variable.

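### SAP 4.1's only rule for results above .05 warns of a type I error, although the risk with a non-significant result is a missed difference, and at the reduced sample size that risk is large

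*SAP*

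**What the plan says.** SAP 4.1 first fixes the Step 1 threshold: "To test our primary hypothesis (H1a), a significance level of .05/3 will be considered as statistically significant in Step 1". For Step 2 it accepts .05 and again uses the term *significance level* for what a test result has to reach. On anything higher, the section has a single instruction, which is the one in question here: "If the significance level is greater than .05, we will emphasis the increased chance of a type I error". It closes by promising 95% confidence intervals with the results but does not say how to read them. SAP 3.4 also promises intervals for differences.

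SAP 6.2 describes the tests. The H1a contrasts use stepwise thresholds of .05/3, .05/2 and .05. For remission (H1b), "Pairwise treatment groups will be compared as in H1a". For SAEs (H2a), "Pairwise comparison between treatment groups will be tested". For falls and fall-related injuries (H2b), "Pairwise comparisons between the treatment group pairs will be formally tested". No alpha is stated for H2a or H2b. The safety hypothesis in SAP 2.2.2, which begins "Augmentation arms will have more tolerability and safety", is directional: it expects more problems with augmentation than with single-drug treatment.

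On sample size, SAP 3.3 says: "Newly adjusted sample size is 708 (estimated mid-study), including 123 participants who were enrolled into step 2 without first participating in step 1". It gives no revised power. Neither document mentions type II error, low power or inconclusive results.

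**The concern.** A type I error can happen only when a null hypothesis is rejected. If the third sentence of 4.1 is about p-values, as the two before it are, it covers results where nothing is rejected. Followed literally, it either attaches an irrelevant warning to a null result or allows a result with p above .05 to be discussed as a finding with a caveat. In both cases the relevant warning, that a real difference may have been missed, is absent.

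The trial compares active strategies and is meant to inform clinicians about relative benefit and harm. After the cut in sample size, inconclusive comparisons are likely even where differences of the size used for planning exist. An interpretation rule that names the wrong error is then a practical problem as well as a slip in terminology.

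**Working it through.** **1. What the sentence can mean.** Three readings were tried.

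- *Alpha above .05.* It is true that a larger alpha raises type I error, but no test in the SAP uses one. The levels are .05/3, .05/2 and .05.
- *p between .05/3 and .05.* The sentence says greater than .05, so it does not cover that range.
- *Uncorrected families of tests.* This is possible, but the sentence mentions neither multiplicity nor secondary tests, and this reading still leaves no rule for a non-significant result.

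The p-value reading fits the neighbouring sentences best.

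**2. Inputs.** From the power table and footnotes in Protocol H2:

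- Step 1: 500 per arm at .05/3.
- Step 2: 400 per arm at .05.
- Remission: base 40%, detectable difference 10.2 points at 80% power in Step 1. The text calls 10 points clinically meaningful.
- SAEs: base 4%, 5.0 points. Fall-related injuries have the same figures.
- Falls: base 20%, 8.8 points.
- Well-being: SD 8 at both times, correlation .5.

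Protocol E 1.b gives 1:1:1 allocation. SAP 3.3 gives 708 − 123 = 585, and 585 / 3 = 195 per arm. Two-sided testing is assumed because it reproduces the table.

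**3. Formula.** For two proportions with n per arm and difference d, let p̄ = (p1 + p2)/2. Then SE0 = √[2p̄(1 − p̄)/n], SE1 = √{[p1(1 − p1) + p2(1 − p2)]/n}, and power = Φ[(d − z·SE0)/SE1]. Here z = 1.960 at .05 and 2.394 at .05/3.

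**4. Reproducing the plan.** At n = 500 and .05/3, SAEs 4% vs 9% give SE0 = .0156, SE1 = .0155 and power Φ(0.817) = .793. Remission 40% vs 50.2% gives .803 and falls 20% vs 28.8% give .802. The table says .8, so the method matches.

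**5. At 195 per arm.**

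| Comparison | SE0 / SE1 | Power at .05 | Missed | Power at .05/3 | Missed |
|---|---|---|---|---|---|
| Remission 40 vs 50% | .0504 / .0501 | .510 | 49% | .340 | 66% |
| SAEs 4 vs 9% | .0250 / .0248 | .517 | 48% | .347 | 65% |
| Falls 20 vs 28.8% | .0435 / .0433 | .525 | 47.5% | .355 | 65% |

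Using 10.2 points for remission changes the power only to .526 and .355. For a 2-point well-being difference, the SD of change is √(64 + 64 − 2 × .5 × 64) = 8, so SE = 8√(2/195) = 0.81. Power is .694 at .05 and .530 at .05/3, which means 31% and 47% missed.

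At .05/3, 80% power at 195 per arm needs differences of 16.3 points (remission), 9.1 (SAEs) and 14.5 (falls).

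**6. Variations.**

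- *Pooled augmentation vs switch* (390 vs 195) at .05: missed 37% (remission), 40% (SAEs), 36% (falls).
- *8% loss* (Protocol K4 assumption), 195 × .92 ≈ 179 per arm: missed 51–52% at .05.
- *All 708 in Step 1* (236 per arm, contrary to SAP 3.3): missed 40–41% at .05 and 57–58% at .05/3.
- *Step 2*, whose size is not given, at .05 with differences of 10, 4.8 and 8.5 points. With 45% remission and 8% dropout, 585 × .47 + 123 ≈ 398, or 199 per arm. With 40% remission among the 92% retained, 585 × .92 × .60 + 123 ≈ 446, or 223 per arm. Between these, 44–50% are missed. Scaling by 800/1,500 without the direct entrants gives 312, or 156 per arm, and 57–59% missed.

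**The case against.** The best defence is that a significance level is, strictly, alpha, and a larger alpha does raise type I error. The sentence is then loose but true. That reading cannot be excluded, but it describes a situation that no test in the SAP creates, and it leaves non-significant results without a rule.

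The second defence is that confidence intervals are already promised. This is real mitigation, but only partial, because nothing says how an interval is to be read when the test does not reject.

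The third is that rewording restores no power. That is correct. The loss comes from the smaller sample, and the sentence matters because it governs how the resulting nulls are described. The miss rates also come from simple two-proportion tests, whereas SAP 6.2 plans a repeated-event Cox model for SAEs and a repeated-measures model for falls, whose power may differ somewhat.

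Three stronger readings are tempting, and the documents do not support them:

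- A reader might infer that at least half of these differences would be missed. At .05, the level in the sentence itself, the Step 1 figures are 47.5–49% without dropout. The 65–66% figures need .05/3, which the SAP sets for H1a and carries to H1b but not to H2.
- A reader might infer that a null H2 result will be reported as no safety difference. No passage says so. H2 is a directional difference hypothesis, and no equivalence or non-inferiority claim is planned. Section 4.1 opens with H1a, so its reach to safety is implied only, although SAP 6.1.1 lists safety under its primary heading.
- A reader might treat 5.0 and 8.8 points as limits for acceptable harm. They are differences detectable with 80% power at 500 per arm. The protocol attaches clinical relevance only to 10 points on remission and 2–3 T-score points.

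**Conclusion.** The point stands as a wrong interpretation rule that should be replaced. On the most natural reading, SAP 4.1 names type I error where type II is the risk, and no other text corrects it. In Step 1 pairwise comparisons, the chance of missing the protocol table's differences in remission, SAEs and falls is about half at .05 and about two-thirds at .05/3. For pooled augmentation versus switch at .05 it is 36–40%. These sizes assume equal arms of 195, two-sided tests, the protocol's base rates and simple two-proportion tests. The test decisions do not change. What changes is how non-significant results are explained.

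**What to change.** Replace the sentence in SAP 4.1 with:

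> If p exceeds the applicable threshold, no difference has been shown; this is not evidence of no difference or of comparable safety, and the chance of a type II error at the achieved sample size will be emphasised. The result will be read from its 95% confidence interval, against the protocol's own relevant differences where it states them (2–3 T-score points for well-being, 10 percentage points for remission). For SAEs, falls and fall-related injuries the interval will be reported and the largest increase in harm it does not exclude will be stated.

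If the present sentence was meant for tests without multiplicity correction, say that separately. State the alpha for H2a and H2b, and give power at the revised sample size. Do not adopt 5.0 and 8.8 points as safety similarity margins.

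The cost is mainly SAP wording. The logit model for remission yields odds ratios, so reading it against 10 percentage points needs one added output, a risk difference with its interval. For the safety outcomes the limit can be stated on the scale of the planned model. The downside is that fewer null results can be worded as reassurance.
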